## **Study Flowchart**

Gastric cancer patients with severe sleep apnea

-> Apply Inclusion/Exclusion Criteria

-> Undergo surgical treatment

-> Decision on prolonging extubation time?

text

Yes -> Exposure Group: Prolonged extubation time

text

No -> Non-Exposure Group: Non-prolonged extubation time

Compare complication rates between the two groups

-> Follow-up for 1 year

-> Compare complication rates between the two groups

## **Data Collection and Management**

Preoperative patient status: General information (name, gender, age, BMI),

preoperative nutritional status, preoperative tumor marker levels, preoperative comorbidities, etc.

Postoperative recovery: Time to recovery of bowel function (first flatus, first oral water/fluid intake), postoperative complications (pulmonary infection, postoperative gastroparesis, postoperative reflux, inflammatory bowel obstruction, bleeding, perforation, anastomosis-related complications such as anastomotic leak, anastomotic stenosis, anastomotic bleeding, etc.), cardiovascular and cerebrovascular complications, etc.

Postoperative follow-up information: Patient review at 1, 3, 6, 9, and 12 months postoperatively, CT and gastroscopy results.

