**Confidentiality Statement:**

The information contained in this study protocol is provided solely to the investigators of this project, the clinical research management committee, and relevant regulatory bodies for review. Disclosing any information to third parties unrelated to this study is strictly prohibited without the approval of the Principal Investigator.

**1. Research Background (State the rationale and significance of this study based on current domestic and international research)**

As one of the most common malignant tumors worldwide, gastric cancer ranks fifth in global cancer incidence and fourth in cancer mortality [1]. Current treatment for gastric cancer is comprehensive, primarily based on surgical treatment, with standard radical gastrectomy being the main procedure [2]. This process is complex, technically demanding, and carries relatively high surgical risks. Obstructive Sleep Apnea (OSA) is a sleep-related breathing disorder characterized by periodic partial or complete upper airway obstruction during sleep, manifesting as apneas and hypopneas [3]. Preliminary statistics indicate the overall prevalence of OSA among adults in China is 3.93% [4], yet the clinical diagnosis rate remains low. OSA is widely recognized as an independent risk factor for hypertension and metabolic syndrome [5, 6]. Reported prevalence of OSA among surgical patients is approximately 7%-10%, but can reach 68%-70% in high-risk populations (bariatric surgery or other major non-cardiac surgery). These patients have significantly increased perioperative complications and mortality [7, 8], especially severe sleep apnea. One cohort study reported the incidence of cardiovascular complications within 30 days after surgery in patients with severe sleep apnea was as high as 30.1% [8]. General anesthesia, sedatives, and postoperative analgesics are potent respiratory depressants; they can relax the upper airway dilator muscles and impair the ventilatory response to hypoxemia and hypercapnia. These effects exacerbate OSA. Concurrently, the hypoxemia caused by OSA can increase the incidence of postoperative complications in gastric cancer patients and may predispose them to postoperative cardiovascular complications [9]. Therefore, for gastric cancer patients with severe sleep apnea, strategies to reduce postoperative complications and adverse events are particularly important.

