**3. Research Methods (This section should be elaborated in detail)**

## **Study Design**

This is a single-center, prospective cohort study. Starting June 2025, the study plans to enroll patients undergoing radical gastrectomy for gastric cancer in the Department of General Surgery of our hospital who also have severe obstructive sleep apnea. Based on the anesthesiologist's assessment during the perioperative period regarding sufficient metabolism of anesthetic agents and full patient awakening, patients will be divided into two groups regarding whether extubation time is prolonged (by 1-2 days): Exposure Group: Prolonged extubation time group; Non-Exposure Group: Non-prolonged extubation time group (extubation on the day of surgery group). Clinical data, intraoperative details, postoperative pathology, lymph node status, and postoperative complications will be recorded for all patients.

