## **Study Outcomes**

Incidence of short-term postoperative complications, graded using the Clavien-Dindo classification.

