## **Sample Size**

The incidence of postoperative complications in gastric cancer patients with severe sleep apnea is the primary endpoint of this study. Based on previous large-scale literature reports, the incidence of perioperative cardiovascular complications in patients with severe sleep apnea undergoing non-cardiac surgery is 15% higher than in the normal population [8]. Using a power of 90% and a significance level of 5%, sample size estimation was performed using PASS, version 11 (NCSS, LLC). We need to recruit 93 patients per group. Accounting for loss to follow-up, dropouts, and other factors, we plan to include 120 patients per group, totaling an estimated 240 patients for both groups.

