### **Statistical Analysis Methods**

Chi-square test or Fisher's exact test will be used to compare categorical variables. Continuous variables will be expressed as median and IQR if non-normally distributed and analyzed using the Mann-Whitney U test, or as mean (SD) if normally distributed and analyzed using the t-test. Survival data will be analyzed using Kaplan-Meier curves. Enrollment is expected to be completed between June 2025 and June 2026. Follow-up is expected to be completed between June 2026 and June 2027.

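### First oral intake is recorded as a marker of bowel recovery, but it cannot precede extubation, so the exposure sets a lower limit on it in the prolonged group only (minor point)

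*Protocol*

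**What the plan says.** Three parts of the protocol's Research Methods section bear on this point.

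- **Data Collection and Management** lists, under postoperative recovery, "Time to recovery of bowel function (first flatus, first oral water/fluid intake"). It gives no time origin, does not say how the two items combine, and does not say when oral intake usually starts.
- **Study Design** defines the exposure: "patients will be divided into two groups regarding whether extubation time is prolonged (by 1-2 days"). The comparator is "Non-Exposure Group: Non-prolonged extubation time group (extubation on the day of surgery group").
- **Statistical Analysis Methods** gives one rule for all continuous variables: "Continuous variables will be expressed as median and IQR if non-normally distributed and analyzed using the Mann-Whitney U test", or a t-test if they are normally distributed. No variable is exempted.

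Bowel recovery is not a named outcome. Study Outcomes lists only "Incidence of short-term postoperative complications, graded using the Clavien-Dindo classification", and Sample Size states: "The incidence of postoperative complications in gastric cancer patients with severe sleep apnea is the primary endpoint of this study".

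**The concern.** The protocol presents first oral intake as a sign that the bowel has recovered. Oral intake also requires that the tube is out, and the time of tube removal is exactly what separates the two groups. For a patient extubated after 1-2 days, the earliest possible value is the extubation time, whatever the state of the bowel. A patient extubated on the day of surgery meets no such limit beyond that day. First flatus, the other item, does not require extubation.

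This bias can run in one direction only: it can make the prolonged group look slower but never faster. Because the variable carries the bowel-function label, a difference produced by the tube would be read as an effect on the bowel. That could appear as an apparent disadvantage of prolonged extubation, or mask a real advantage, in the recovery results.

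**Working it through.** The protocol states no figure for bowel recovery, so there is none to reproduce. The check is how often the lower limit alone would produce a significant difference.

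**Inputs from the protocol**

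- Delay of extubation in the exposed group: 1-2 days (Study Design).
- Planned group size: 120 per group (Sample Size).
- Test: Mann-Whitney U (Statistical Analysis Methods).

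**Assumptions, not in the protocol**

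- The time T from surgery to first oral intake, if no tube were in the way, has the same lognormal distribution in both groups, with log-SD 0.4.
- The usual median m of T is varied from 0.5 to 5 days.
- Extubation time F in the exposed group is uniform on 1 to 2 days.
- The test is two-sided at the 5% level.

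**Model**

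- Comparator: observed time = T.
- Exposed: observed time = max(T, F).

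The tube thus delays only those patients who would otherwise have drunk before extubation.

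**Share of exposed patients delayed.** At a given extubation time f this is P(T < f) = Φ(ln(f/m)/0.4), averaged over f from 1 to 2. Simpson's rule on f = 1, 1.5 and 2 gives:

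- m = 1 day: (0.500 + 4 × 0.845 + 0.958)/6 = 0.81
- m = 2 days: (0.042 + 4 × 0.236 + 0.500)/6 = 0.25
- m = 3 days: (0.003 + 4 × 0.042 + 0.155)/6 = 0.05

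These agree with the simulated shares below to within rounding.

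**Simulation** (1000 studies per row, no true difference in recovery)

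| Usual median intake (days) | Exposed patients delayed by the tube | Mean difference in medians (days) | Studies with p < 0.05 |
|---|---|---|---|
| 0.5 | 99% | +1.00 | 100% |
| 1 | 80% | +0.57 | 100% |
| 1.5 | 48% | +0.25 | 94% |
| 2 | 25% | +0.02 | 20% |
| 3 | 5% | -0.01 | 6% |
| 4 | 1% | -0.01 | 5% |
| 5 | 0% | -0.01 | 5% |

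The last three rows are at the nominal 5% level within simulation error. The false-positive rate therefore runs from certain to nominal, and the parameter that decides it is the usual time of first oral intake.

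**The case against.** The strongest case on the other side has three parts.

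1. **The variable is peripheral.** Bowel recovery appears once, in a list of data to be collected. The objective, the hypothesis, Study Outcomes, Sample Size and the flowchart all concern complications. The link to a between-group test is a general sentence on continuous variables, and nowhere does the protocol say that a difference would be read as harm. This stands, and it is why the point is minor. A reader might infer that a study outcome is biased; the documents do not support that.

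2. **A lower limit is not a delay.** A reader might infer that prolonged extubation delays this measure by construction, for example by adding one or two days to every exposed patient. That does not follow. The tube delays only patients who would otherwise drink before extubation. If intake after gastrectomy usually starts later than the 1-2 day window, the tube delays almost nobody. The protocol does not give that timing, so a delay cannot be asserted unconditionally. Figures obtained by shifting every exposed patient by a fixed amount would presuppose the result. This also stands.

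3. **It is only labelling, and an analysis plan can settle it.** Flatus and oral intake are named as two items, no composite is defined, and extubation time is already collected as the exposure. Much of the remedy is therefore at hand. But the protocol itself states what first oral intake is taken to mean, and that stated meaning is what would turn a difference caused by the tube into an apparent bowel effect. This part does not remove the point.

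**Conclusion.** The point holds as a minor one. First oral intake has a lower limit set by the exposure in the prolonged group and none beyond the day of surgery in the comparator. It is therefore a poor marker of bowel function for this comparison, and any bias from this source runs against the prolonged group.

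Whether the bias is material cannot be decided from the protocol. Under the assumptions above, it is severe if intake would usually start within about 1.5 days of surgery, modest at 2 days and absent from 3 days. These figures are illustrative: only the 1-2 day range, the group size and the test come from the protocol. The assumed spread of intake times, and the assumption that a delayed patient drinks at the moment of extubation, both affect the intermediate rows.

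The primary complication endpoint is not affected by this point.

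**What to change.** In Data Collection and Management:

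- For the between-group comparison, define recovery of bowel function by first flatus, timed from end of surgery.
- Report first oral intake as a separate descriptive variable, timed both from end of surgery and from extubation.
- State that first oral intake is not interpreted as bowel function between the groups.

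The cost is about one sentence. No new data item is needed beyond the clock times of items already collected, since extubation time is the study's own exposure. The downside is one fewer component in the bowel-recovery measure. The change concerns measurement and interpretation only and implies nothing about when patients should be extubated or fed.

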### **Statistical Analysis Methods**

Chi-square test or Fisher's exact test will be used to compare categorical variables. Continuous variables will be expressed as median and IQR if non-normally distributed and analyzed using the Mann-Whitney U test, or as mean (SD) if normally distributed and analyzed using the t-test. Survival data will be analyzed using Kaplan-Meier curves. Enrollment is expected to be completed between June 2025 and June 2026. Follow-up is expected to be completed between June 2026 and June 2027.

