### **Study Abstract**

Item	Content
Project Title	An Exploratory Study on the Impact of Prolonged Postoperative Endotracheal Extubation Time on Postoperative Complications in Gastric Cancer Patients with Severe Obstructive Sleep Apnea
Study Objective	To investigate the impact of prolonging the time to postoperative endotracheal extubation on the incidence of postoperative complications in gastric cancer patients with severe obstructive sleep apnea.
Research Hypothesis	Prolonging the time to endotracheal extubation in gastric cancer patients with severe obstructive sleep apnea can reduce the incidence of postoperative complications.
Study Design	 Case-Control Study  Cohort Study 

Item	Content
Cross-Sectional Study	
	 Case Report / Case Series
Inclusion Criteria:	
 
1. Patients preoperatively diagnosed with resectable gastric cancer.
 
2. Patients without distant organ metastasis.
 
3. Patients with preoperative OCST or PSG results showing AHI >30 events/hour and Sa02 <80%.
 
4. Patients with cardiopulmonary function deemed suitable for surgery.
 
5. Patients aged 18–85 years.
 
6. Patients who voluntarily joined this study and provided written informed consent.
 

Exclusion Criteria:	
 
1. Patients with a history of or concurrent other malignant tumors.
 
2. Patients who underwent palliative resection.
 
3. Subjects who experienced acute cardiovascular or cerebrovascular events (e.g., acute cerebral infarction, acute coronary syndrome) within the past 3 months, or whose cardiovascular clinical symptoms/diseases are not well-controlled.
 
4. Patients with a history of psychotropic drug abuse that cannot be abstained, or those with psychiatric disorders.
 
5. Patients with concomitant diseases that, in the investigator's judgment, seriously endanger the patient's safety or affect the completion of the study.
 

Meet either (A + B) or C below.	

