**2. Research Question & Objectives (Elucidate the scientific question and research objectives)**

To investigate the impact of prolonging the time to postoperative endotracheal extubation on the incidence of postoperative complications in gastric cancer patients with severe obstructive sleep apnea.

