### **Inclusion Criteria:**

Patients preoperatively diagnosed with resectable gastric cancer.

Patients without distant organ metastasis.

Patients with preoperative OCST or PSG results showing AHI >30 events/hour and SaO2 <80%.

Patients with cardiopulmonary function deemed suitable for surgery.

Patients aged 18-85 years.

Patients who voluntarily joined this study and provided written informed consent.

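### A causal question in a non-randomised cohort is paired with crude two-group tests only, so the reasons for prolonging extubation are left uncontrolled

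*Protocol*

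**What the plan says.** The Study Abstract hypothesises that later extubation in gastric cancer patients with "severe obstructive sleep apnea can reduce the incidence of postoperative complications". Section 2 sets the aim: "To investigate the impact of prolonging the time to postoperative endotracheal extubation on the incidence of postoperative complications". Both are causal statements.

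Study Design describes a single-centre prospective cohort in which "patients will be divided into two groups regarding whether extubation time is prolonged (by 1-2 days". It ties this to the anaesthesiologist's "assessment during the perioperative period regarding sufficient metabolism of anesthetic agents and full patient awakening". The Study Flowchart shows the groups splitting after surgery on a yes/no decision to prolong, followed by a comparison of complication rates.

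Statistical Analysis Methods states that a chi-square or Fisher's "exact test will be used to compare categorical variables", and names the t-test or Mann-Whitney test for continuous ones and Kaplan-Meier curves for survival data. The Study Abstract gives the same list without Kaplan-Meier. Neither place labels a primary test, and neither mentions regression, propensity scores, matching, weighting, stratification or a list of confounders.

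Data Collection and Management lists age, gender, BMI, nutritional status, tumour markers and comorbidities, with no stated role in the analysis. It lists neither the awakening assessment nor the reason for prolonging.

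**The concern.** The sentence in Study Design can be read in two ways. The awakening assessment may be the criterion that assigns the group, or the reference point from which prolongation is counted. On either reading patients are selected into the groups by clinical judgement, so the groups may differ in prognosis before the exposure begins.

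Complication incidence is categorical, and the only named test that fits it is chi-square or Fisher's exact. Followed as written, the plan attributes every baseline difference in risk to the extubation policy. If higher-risk patients are kept intubated, a real benefit is masked or harm appears. If lower-risk patients are kept intubated, a benefit is manufactured. This is the study's only primary comparison, and its result could be read as evidence for or against keeping patients intubated for a further one to two days.

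**Working it through.** **The plan's own figure.** Sample Size gives 93 per group before losses (120 planned) at 90% power and a 5% level, citing a 15% difference without two explicit rates. The one event rate in the document is 30.1% (Research Background). With 30.1% against 15.1%, two-sided:

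n = [1.960·√(2·0.226·0.774) + 1.282·√(0.301·0.699 + 0.151·0.849)]² / 0.15² = 162 per group.

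So 93 is not reproduced from the document's figures. That is a separate matter. It enters here only because the cost figures under the fix take 93 as given.

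**Size of the bias.** The documents give no inputs for this, so the following values are assumed to show the mechanism:
- one binary risk marker, with complication risk 40% if present and 20% if absent;
- 120 patients per group;
- marker share in the prolonged / same-day group of 60/40 or 70/30, and the reverse.

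Crude risk in a group = share·0.40 + (1 − share)·0.20. For example, at 70/30 with no effect: 0.7·0.4 + 0.3·0.2 = 0.34 against 0.3·0.4 + 0.7·0.2 = 0.26. Under a true effect, risk is halved in the prolonged group. Rejection rates are exact binomial probabilities for the two-sided 5% chi-square test.

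| Marker share, prolonged / same-day | Crude risks, no effect | False significance | Crude risks, risk halved | Crude power | Expected events, halved |
|---|---|---|---|---|---|
| 50/50 | 30% vs 30% | 5% | 15% vs 30% | 81% | 54.0 |
| 60/40 | 32% vs 28% | 10% | 16% vs 28% | 62% | 52.8 |
| 70/30 | 34% vs 26% | 27% | 17% vs 26% | 40% | 51.6 |
| 40/60 | 28% vs 32% | 10% | 14% vs 32% | 92% | 55.2 |
| 30/70 | 26% vs 34% | 27% | 13% vs 34% | 98% | 56.4 |

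The false findings run almost wholly one way. At 70/30 the 0.271 is 0.271 towards harm and 0.0005 towards benefit, and the reverse imbalance mirrors this. The 92% and 98% are power inflated by bias.

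**What adjustment recovers.** Mantel-Haenszel test stratified on the marker, 20,000 simulated studies per setting:
- Marker recorded perfectly: false significance about 5%; power with risk halved 80% (60/40 and 40/60) and 74–75% (70/30 and 30/70).
- Marker recorded with 80% sensitivity and specificity: false significance about 7% (60/40 and 40/60) and about 15% (70/30 and 30/70).

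Adjustment therefore reduces the bias, but removes it only as far as the confounders are well measured.

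**The case against.** The strongest objection is that only the protocol is available. A covariate list and an adjusted model are often left to an SAP, and the methods paragraph assigns generic tests by variable type without stating that nothing else will be done. That is why the crude primary test is described as an inference. It does not remove the point: the protocol is not silent, since it states its methods in two places and those methods do not answer its question. Nor can a later SAP recover data never collected. The open-ended list in Data Collection and Management, and the promise in Study Design that "Clinical data, intraoperative details, postoperative pathology, lymph node status, and postoperative complications will be recorded for all patients", might cover the reason for prolonging, but neither guarantees it.

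The study is also titled exploratory and called observational, and eligibility narrows the prognostic spread (severe apnoea only; recent or uncontrolled cardiovascular disease excluded). Yet a directional hypothesis and a 90% power statement stand beside the exploratory label, and narrowing the population does not balance the groups within it.

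It is also fair that every bias figure is assumed; they show how the error arises and do not estimate it for this study. Overlap weighting is one reasonable choice among several and changes the target population, which must be stated.

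**Conclusion.** The concern holds and must be fixed. The protocol poses a causal question, forms its groups by clinical decision, and names no method that controls for why a patient was in one group rather than the other. Under the assumed marker, the nominal 5% error becomes 10% or 27%. Power for a true halving of risk falls from 81% to 62% or 40%, or is inflated to 92% or 98%, depending on which group carries more risk. These figures rest on assumed risks and imbalances. That the comparison is confounded if run as stated rests on the text alone, together with the inference that the named categorical test is the primary one.

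**What to change.** Make a pre-specified confounder-adjusted comparison primary. A workable choice is propensity-score overlap weighting, reporting a risk difference with 95% CI and stating that the effect refers to the overlap population. Use logistic regression with a standardised risk difference as sensitivity analysis.

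- **Covariates**, all fixed before the extubation decision: age, sex, BMI, comorbidities and nutritional status; the AHI and SaO2 values behind the eligibility criterion ("preoperative OCST or PSG results showing AHI >30 events/hour" and its saturation limit); and named items from the intraoperative record.
- **Two added database fields:** the awakening assessment, and the reason for prolonging. The reason describes selection and is not an adjustment covariate.
- **Model size:** the propensity model can carry the full list. An outcome model cannot: with about 52–56 events in the illustrated halving scenarios and an assumed 10 events per parameter, it supports about 5 parameters, so its reduced set must be named in advance.
- **Reporting:** show balance and overlap. If the awakening assessment fully determines the group there is no overlap, and no adjusted effect should be claimed. Keep the crude chi-square as descriptive, and word the conclusion as an association because unmeasured confounding remains.

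**Cost.** More analysis work, two fields, no new procedures, and some loss of precision. The stated 90% power should not be carried over without recalculation. Taking 93 per group as given, and using n/(1 − R²) as a rough guide with R² the squared correlation of exposure and marker:
- 60/40: R² = 0.2² = 0.04; 93/0.96 = 96.9, so 97 per group.
- 70/30: R² = 0.4² = 0.16; 93/0.84 = 110.7, so 111 per group.

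The margin for losses within 120 falls from (120 − 93)/120 = 22.5% to (120 − 97)/120 = 19.2% or (120 − 111)/120 = 7.5%. If the covariates explain more than 22.5% of the exposure, 120 per group is too few even with no losses.
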